### 14.1.4 Data analysis

Descriptive statistics for all parameters will be calculated. For continuous parameters descriptive statistics including mean, standard error, median, minimum, and maximum values will be reported overall and at each time-point. For ordinal parameters, counts and percentages may be reported in addition to the mean, standard error, median, minimum, and maximum values. Categorical parameters will have counts and percentages reported overall and at each time-point.

### 14.1.5 Interim Review of Data

An interim report may be generated depending on rate of enrollment and completeness of study data generated from patients enrolled. It is anticipated that enrollment will be conducted quickly and the potential timing for an interim analysis may not be feasible.

	Document Title	Clinical Investigational Plan For Study CL-SY-02-0096		
	Document No.	DOC001593	Revision	03

## 15 SAFETY CONSIDERATIONS

### 15.1 Safety Parameters

#### 15.1.1 Risks Associated with Participation In The Clinical Investigation

The risks associated with the C-Scan system are similar to those risks associated with regular Capsule Endoscopy. Risks associated with both Capsule Endoscopy and the Colon Capsule include but not limited to the following: constipation or diarrhea, capsule delay or retention throughout the GI tract, erosion of the colon mucosa, allergic reaction to the ingested contrast material, pain and discomfort.

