### 10.4 Secondary Outcome Measures

- Subject compliance will be assessed by
  - Non-compliance rate throughout the study via diary completion by the subject Specific questionnaire completed by remote subject monitoring (via telephone)
- Subject satisfaction will be established by:
  - Designated questionnaire that focuses on patient's impressions regarding tolerance and potential safety concerns. Acceptance criteria was defined as average score >3.5 (1- low satisfaction to 5- high satisfaction), which represent high satisfaction with the safety and tolerance of the C-scan system.
  - Comparing patient's satisfaction with colonoscopy procedure.
- Collecting procedure related data:
  - Technical performance in normal daily routine.
  - Segmental transit time.
  - Procedure duration.
  - Bowel movements.
  - Agreement between C-Scan and colonoscopy with respect to the presence/absence of colonic polyp(s) [Note: C-scan data not to be used for clinical decision making in the care of patients, for this clinical study].
  - Inter-observer variability in the detection of significant clinical findings on a 'per patient' decision
- Battery life Assessment
  - Assessing adequate power supply for complete scan of the colon: length of capsule operation lifetime with respect to the lifetime specification of 100 +/- 10% hours.
- Device performance
  - Assessing colon model by the physician reviewers as presented on C-Scan View (e.g., normal, partial, right side missing, etc.).
  - Collecting data to improve the product's algorithm.

	Document Title	Clinical Investigational Plan For Study CL-SY-02-0096		
	Document No.	DOC001593	Revision	03

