## 11 STUDY DESIGN

### 11.1 Overall Design

Up to 45 healthy subjects will participate in this study. Subjects to be enrolled in this study are indicated and scheduled to undergo optical colonoscopy based on the following symptoms or by being classified as higher than average risk based on one or more of the following:

- Surveillance - Significant findings in previous optical colonoscopy
- Diagnostic - Polyps detected in virtual colonoscopy referred for polypectomy
- Diagnostic - Polyps detected in previous optical colonoscopy (community setting) referred for polypectomy
- Diagnostic - Positive FIT test
- Diagnostic – one or more of the typical symptoms:
- abdominal pain
- Change in bowel habits
- Anemia or overt bleeding in stool
- Significant weight loss
- First degree relatives of CRC subjects

Alternatively, average risk based on their age and demographics referred for screening for polyps

Each subject will receive a comprehensive explanation regarding the study nature. During this process, and per ethical committee approval, subjects may be asked several questions (over the phone) regarding their medical background for preliminary assessment of eligibility. Once informed consent is obtained, a thorough evaluation of subject's eligibility will be performed based on inclusion / exclusion criteria. Eligible subjects will be required to undergo FIT procedure, per package insert instructions, within pre-defined timelines. All subjects will be scheduled to undergo capsule procedure, to be followed later on with optical colonoscopy procedure.

One to three days following end of C-Scan procedure the subjects will be contacted by phone by the clinical coordinator to follow-up on the subject well-being. Same follow-up procedures will be applied one to three days following Optical Colonoscopy procedure. Medical history and concomitant medication information will be collected for all subjects.

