## 12.4 Withdrawal Criteria

Subjects may withdraw from the study at their own request at any time.

The investigator may withdraw a subject from the study at any time for the following reasons:

- a. Severe side effects clearly related to the study device or procedure
- b. Less than adequate compliance with the study routine
- c. Presence or appearance of exclusion criteria
- d. Refusal to undergo 'post' colonoscopy
- e. A significant protocol violation
- f. At the specific reasonable request of the sponsor

The sponsor must be informed in each withdrawal case within 24 hours. The reason for withdrawal has to be recorded in the subject's file.

CONFIDENTIAL

The information contained in this document is confidential and the sole property of "Check-Cap"  
Any reproduction in part or whole without the written permission of "Check-Cap" is prohibited

	Document Title	Clinical Investigational Plan For Study CL-SY-02-0096		
	Document No.	DOC001593		Revision 03

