### 13.2 Study Documentation

The following documents and information will be collected:

- Completed Visit and Follow-up Case Report Forms (CRFs)
- Referring procedure report (optical colonoscopy or virtual colonoscopy), if applicable
- FIT Results (+ photo)
- Subject's diary with all daily activities during home procedure
- Subject's usability questionnaire
- Subject Satisfaction Questionnaire
- C-Scan procedure raw data
- C-Scan report
- Optical Colonoscopy report
- Video recording of Optical Colonoscopy
- Pictures of Optical Colonoscopy, if taken
- Copy of pathology report, if conducted

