### **13.8 Follow-Up 3: Post-Colonoscopy Procedure**

Subject will be telephoned by study site to assess subject satisfaction with the colonoscopy procedure as compared to the C-Scan. Follow up window is 1-3 days post-colonoscopy. Additionally, the BBPS and colonoscopy report will be collected from the test site for comparative analysis with the C-Scan procedure. The subject will be exited from the study upon completion of this follow-up

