## 16.2 Anticipated Adverse Events

The following events are known potential adverse events from the C-Scan procedure. They will be reported as adverse events for the purposes of the study:

- Delayed C-Scan Capsule excretion
- Capsule retention
- Change in bowel habits
- A small amount of fresh blood in the stool
- Potential difficulty swallowing the capsule
- Abdominal discomfort during the passage of the capsule
- Abdominal pain, cramps
- Back pain
- Nausea
- Loss of appetite
- Soft/runny stool
- More than 2/day bowel movements
- Diarrhea
- Constipation
- Allergic reaction to the ingested contrast material
- Skin irritation caused by the stickers on back
- Impaired night sleep caused by the C-Scan track (recorder on the back)
- Excessive radiation exposure (> 200 [ uSv] microSivert) Note: This threshold was calculated as 2X the max body dose in a long, but normal, procedure: total transit time of 100 hours and with 4000 scanning pages, which is the maximum ever reached during a normal procedure.

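### Section 15.1.1 names erosion of the colon mucosa as a capsule risk, but the colonoscopy report collected afterwards feeds no safety variable, so a symptomless lesion has no planned route into the adverse event data

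*Combined protocol and SAP*

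**What the plan says.** Section 15.1.1 describes the C-Scan risks as similar to those of capsule endoscopy and lists, among others, "capsule delay or retention throughout the GI tract, erosion of the colon mucosa, allergic reaction to the ingested contrast material". Section 15.1.4 adds that the emitted radiation could harm the colon.

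Section 16.2 introduces its list with "The following events are known potential adverse events from the C-Scan procedure". Fresh blood in the stool, abdominal pain and contrast allergy are on it. Mucosal erosion is not.

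On the examination after the capsule, section 11.1 says "All subjects will be scheduled to undergo capsule procedure, to be followed later on with optical colonoscopy procedure". The exception is in 12.4, where "Refusal to undergo 'post' colonoscopy" is a ground for withdrawal. Section 13.2 lists the colonoscopy report and "Video recording of Optical Colonoscopy" among the items to be kept. Section 13.8 says that "the BBPS and colonoscopy report will be collected from the test site for comparative analysis with the C-Scan procedure".

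On AE collection, section 16 has subjects asked about reactions at each visit or call, and does not collect events whose onset follows the start of bowel preparation. Section 16.4.1 exempts the colonoscopy visit and its preparation from AE enquiry. In both copies of the schedule (section 5 and Table 1 in 13.1) the AE row has no mark at Follow-up 3.

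**The concern.** An erosion is mainly something seen. A subject on the telephone can report it only if it hurts or bleeds. The one planned look at the colon wall after the capsule has passed is the colonoscopy, and the plan sends its findings to the device comparison and to no safety variable.

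The primary objective is safety. If the plan is followed to the letter, the AE tables will say nothing about symptomless injury of a kind that the protocol itself names, while the relevant reports are already on file. A reader of an AE table without erosions could not tell whether none was seen or none was asked about.

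**Working it through.** The plan gives no figure to reproduce. Section 14.1.1 says that the sample size is not based on power, and 14.1.4 is descriptive. The check is a comparison of sections, followed by an illustration of size.

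**Is there a planned route?**

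1. *Named harm.* Erosion is in 15.1.1 and missing from 16.2. The two lists do not match.
2. *Uses of the colonoscopy findings.* 10.4: agreement with C-Scan on polyps. 13.8: report and bowel preparation score, for comparison with the C-Scan procedure. 13.10: C-Scan findings set against FIT and colonoscopy. Satisfaction with the two procedures is also compared. None of these is a safety use, and no section asks the endoscopist, the readers or the adjudicator to record mucosal injury.
3. *How AEs are found.* By asking subjects (sections 16, 13.6.4 and 16.4.1) and by a question in the usability questionnaire (13.7.2). Neither reveals a symptomless lesion.
4. *Contact at and after colonoscopy.* 16.4.1 removes AE enquiry from the colonoscopy visit. The schedule leaves the AE cell blank at the Follow-up 3 call, although section 16 has subjects asked at each phone contact. These places need reconciling in any case.
5. *Possible substitutes.* FIT is done before or during the capsule procedure (13.6.1). Subjects may enter because of a positive FIT or overt bleeding (11.1), so blood in the stool cannot be tied to the capsule.
6. *Is reporting forbidden?* No. The AE definition in 16.1.1 covers signs, whether or not related to the device. The section 16 cut-off is by onset, and a capsule lesion would begin before preparation. Section 16.3 has unanticipated events reported too, and 17.1 treats the colonoscopy report as a source document.
7. *Primary outcome.* Section 10.3 counts related serious adverse events. A symptomless erosion would rarely meet any criterion in 16.1.2.

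**Illustration of size**

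Inputs: n = 45, the maximum in 14.1.1, and n = 30 as an assumed lower number of available reports. The true rates p of lesions visible at colonoscopy are assumptions.

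Chance of at least one case = 1 − (1 − p)^n. For n = 45 and p = 5%: 1 − 0.95^45 = 1 − 0.099 = 0.901.

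Exact two-sided 95% upper limit for zero cases = 1 − 0.025^(1/n). For n = 45: 1 − 0.9213 = 0.0787. For n = 30: 1 − 0.8843 = 0.1157.

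| Assumed rate p | Expected cases, n = 45 | P(at least one), n = 45 | P(at least one), n = 30 |
|---|---|---|---|
| 1% | 0.45 | 36% | 26% |
| 2% | 0.90 | 60% | 45% |
| 5% | 2.25 | 90% | 79% |
| 10% | 4.50 | 99% | 96% |

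Upper limit for zero cases: 7.9% with 45 reports, 11.6% with 30.

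**The case against.** The strongest reply is that an erosion recorded in the colonoscopy report is already a reportable AE. The definition is broad, absence from 16.2 excludes nothing, the cut-off goes by onset, and the sponsor receives the report. This stands against the inference, which a reader might draw, that a symptomless injury cannot enter the safety data at all. The documents do not support that inference; what is missing is a prompt and a rule for dating and attribution. Section 16 also says that colonoscopy-related events are not reported, so without such a rule a site could easily leave the lesion out.

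Second, the primary result would hardly move, because a symptomless erosion is seldom a serious event. This stands and limits the point to the supporting AE data.

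Third, 13.8 does not confine its comparison to polyps, and the CRF is not among the documents, so its colonoscopy page may already have a field for other findings. Both are fair. Even so, no section makes such a field a safety variable.

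Fourth, attribution is weak. No colonoscopy before the capsule is required (a previous report is collected if available), and some subjects enter with bleeding, anemia or a positive FIT (11.1). Preparation or drugs can also cause erosions. The colonoscopy need only be scheduled within 60 days (12.2), with no interval from the capsule fixed, so lesions may have healed. All of this stands. It argues for reporting the finding descriptively with its limits.

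Fifth, events listed for the previous study (8.1) include no mucosal erosion. The documents do not say whether it was looked for, so this settles nothing.

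**Conclusion.** The point holds as a gap in safety ascertainment. A harm named in 15.1.1 is missing from 16.2, and the examination that could show it feeds no safety variable. Under the plan as written, planned capture of symptomless mucosal lesions is nil whatever their true rate; any that are recorded would depend on an investigator's initiative.

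The consequence is confined to the AE data that support the safety objective. A reader might infer that the primary safety result is compromised. The documents do not support that, since the primary outcome counts related serious events and these lesions would rarely qualify.

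The size cannot be fixed from the documents, because they give no lesion rate. Across assumed rates of 1% to 10%, the chance that 45 reports contain at least one case runs from 36% to 99%. The 7.9% upper limit for zero of 45 assumes that all 45 reports are available and record such lesions reliably. It would describe lesions visible at the time of colonoscopy and would not bound all capsule injury. This is a low-cost improvement to an unpowered, descriptive pilot.

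**What to change.** - Add mucosal erosion to 16.2, so that it agrees with 15.1.1.
- Add one CRF item, completed from the colonoscopy report already collected: mucosal erosion, ulcer, haematoma or bleeding point recorded (yes/no), segment, and the investigator's judged cause.
- State that such a lesion, when not attributed to the colonoscopy, its preparation or known pre-existing disease, is recorded as an AE with onset before bowel preparation. Reconcile this with section 16, section 16.4.1 and the blank AE cell at Follow-up 3.
- Report n/N among subjects with a colonoscopy report, with an exact 95% confidence interval and the days from capsule excretion to colonoscopy, as a descriptive result separate from the primary outcome. State the limits on attribution and healing beside it.

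The cost is one CRF item, one list entry and a short protocol text. No extra procedure or visit is needed. The videos should not be re-read for this purpose, since that would need a reader. The price of relying on the report is that only lesions the endoscopist chose to record will be counted.

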#### 15.1.2 Potential Risk From The Capsule Procedure

- Delayed excretion or retention of the capsule in the GI tract
- Exposure to low dose X-ray radiation during the capsule passage and from the abdominal X-ray (if required, post questionable excretion)
- Exposure to low level electromagnetic radiation
- Change in bowel habits or abdominal discomfort during the passage of the capsule
- Unexpected capsule related Adverse Events

#### 15.1.3 Capsule Retention

There is a low risk of capsule retention, *i.e.*, no excretion of the capsule after more than 300 hours (defined as SAE). Delayed capsule excretion is defined as no excretion of the capsule after 100 hours (approximately 4 days). In some instances, intervention is required to remove the capsule. Intervention, based on the physician's decision and imaging of the capsules location may include: use of laxatives, non-soluble fiber supplements, removal by colonoscopy or surgery.

##### 15.1.3.1 Possible Scenarios and Recommended Physician's Action:

In all cases the physician may opt to use local protocols for patients administered with gastrointestinal capsules; medical intervention or lack of, which remains at physician's discretion.

- **Capsule is Not Found After C-Scan® Track indicates it was expelled**
  - Advise the subject to look in the toilet. If it is found, the subject should notify the clinic which will arrange for the collection of the C-Scan system.
  - If the capsule is not found, the subject should speak with a physician at the clinic as there is a chance it was not expelled despite the positive indication. The physician might recommend using a laxative at home to try to expel the capsule. Make sure that the subject knows to use the collection kit during any bowel movements. Or, the physician investigator may recommend the subject to come to the clinic for a physical exam, and depending on findings, consider abdominal X-Ray imaging.
- **Capsule Not Expelled After 4 Days (~100 hours)**
  - If 4 days have passed and the capsule was not expelled, the subject should speak with a physician at the clinic (if needed, be sure to initiate a contact with the patient). The physician might recommend using a laxative at home to try to expel the capsule. Make sure that the subject knows to use the collection kit during any bowel movements. Or, the physician investigator may recommend the subject to come to the clinic for a physical exam, and depending on

	Document Title	Clinical Investigational Plan For Study CL-SY-02-0096		
	Document No.	DOC001593	Revision	03

findings, consider abdominal X-Ray imaging.

- Intervention, based on the physician's decision and imaging of the capsule's location, may include: use of laxatives, fibers, removal by colonoscopy, or by surgery.
- In case that the capsule is retained in the small bowel, as suspected according to the X-Ray imaging, the recommended Intervention, based on the physician's decision, may include: use of laxatives, prokinetic drugs, removal by SB enteroscopy (with double balloon if available) or by surgery.

- **Capsule lost communication (no flashing lights on Track) at any time between ingestion and 100 hours:**
  - Advise the subject to verify that the batteries in the Track are in position and the compartment is well secured
  - Verify that the patient is still wearing the Track on his/her back
  - If communication is still interrupted or missing, contact the technical support to consult about potential malfunctions and interventions.
  - If the problem is not resolved and the communication is missing - have the patient come to the clinic
  - There is no reason to assume there is a safety malfunction, but since the procedure is not yielding any additional valuable clinical data, it is recommended to take steps to expel the capsule out.
  - The clinic team (technician and/or physician) should perform, in case the capsule has not been excreted and collected already, abdominal X-Ray to assure the capsule location within the GI tract.
  - Intervention, based on the physician's decision and imaging of the capsule's location, may include: use of laxatives, fibers, removal by colonoscopy, or by surgery.
- **Technical Malfunction – C-Scan® Track Sent a Fault Indication**
  - Verify that the auditory indication was from the C-Scan® Track and not a background noise. A C-Scan® Track safety fault indication is identified by a series of repeated beeps.
  - Ask the subject if a single indication was received, or was it repeated at regular intervals.
  - Ask if the subject feels any discomfort.
  - If it is a Safety malfunction (risk of higher than usual body radiation exposure), have the subject come to the clinic ASAP and no later than 48 hours post call.
  - If the capsule has not already been excreted and collected, the clinic team (technician and/or physician) should perform abdominal X-Ray to assure the capsule location within the GI tract.
  - In the case of Safety Malfunction, intervention is required to remove the capsule without delay (recommended within 24 hours). Intervention, based on the physician's decision and imaging of the capsule's location, may include: use of laxatives, fiber supplements, removal by colonoscopy, or by surgery.

	Document Title	Clinical Investigational Plan For Study CL-SY-02-0096		
	Document No.	DOC001593	Revision	03

- Efforts should be made to minimize the subject's exposure by removing the capsule out of the body.

#### **15.1.4 Low X-Ray Body dose**

In addition, the capsule emits low level X-Ray radiation for a few seconds each time it scans the colon. The major source of radiation dose is from Ta182, a byproduct contaminant.

The radiation may potentially cause damage to the colon or nearby organs. Based on calculations the radiation dose level is rather low: 100 times lower than CT Colonography or similar to the radiation your body absorbs while flying from Europe to New York (8 hour flight = 0.06 mSv).

Once the capsule is excreted, the risk of radiation is eliminated.

	Document Title	Clinical Investigational Plan For Study CL-SY-02-0096		
	Document No.	DOC001593	Revision	03

## 16 ADVERSE EVENTS

Subjects will be carefully monitored for adverse events. Subjects will be guided to report if they feel any pain or discomfort during the trial. At each visit or phone contact, subjects will be asked if they experienced any adverse reaction since the last visit.

Any adverse events with an onset following beginning of bowel preparation to colonoscopy procedure will not be collected. Colonoscopy related adverse events are not part of the study, are considered standard of care and will not be reported.

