### 10.3 Primary Safety Outcome Measure

The safety of the Check-Cap System will be evaluated by the incidence of device or procedure related Serious Adverse Events (SAE), as adjudicated by the Independent Physician Adjudicator.

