### 16.1 Adverse Event Definitions

#### 16.1.1 Adverse Event

An Adverse Event is any unwanted medical occurrence in a subject (e.g. sign, symptom, illness, abnormal laboratory value, or other medical event) occurring to a subject that appears or worsens during a clinical study, whether or not considered related to the device.

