## 16.3 Recording and Documentation of Adverse Events

All adverse events should be evaluated by the Investigator, and should be medically handled per investigator discretion. All adverse events shall be recorded in the subject's Adverse Event Case Report Form. The following data should be carefully documented:

- Subject's study ID/code
- Type of event
- Time of occurrence (i.e. date & time)
- Time of resolution (i.e. date & time)
- Severity degree (mild/moderate/severe/unknown)
- Relationship to study device (definitely/probably/possibly/probably-not/not-related)
- Measures taken (e.g. concomitant medication, hospitalization, etc.)
- Event outcome (unchanged/worsened/improved/resolved/unknown/death)

Adverse events will be assessed in terms of seriousness, duration, intensity and relationship to the study device and/or procedure. All anticipated and unanticipated adverse events will be collected and reported.

	Document Title	Clinical Investigational Plan For Study CL-SY-02-0096		
	Document No.	DOC001593	Revision	03

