## **16.4 Safety Reporting Procedures**

### **16.4.1 Adverse Events Reporting**

Subjects are encouraged to report any event to the study team and consult the PI for any change in their well-being. Subjects will be asked for any change in their medical condition during each study visit or phone call with the exception of Visit 2 for the standard of care Colonoscopy and the associated preparation procedure.

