### **16.4.2 Serious Adverse Events Reporting**

Serious adverse events shall be reported to Check-Cap/Clinical Research Organization (CRO) in writing (using the Serious Adverse Events Form taken from the CRF) within 24 hours of the investigator's awareness of the event, and should be reported to the local Ethical Committee per their requirements.

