### **16.4.3 Unanticipated Adverse Device Effect Reporting**

Unanticipated adverse device effects shall be reported to Check-Cap/CRO in writing (using the Serious Adverse Events Form taken from the CRF) within 24 hours of the investigator's awareness of the event.

Check-Cap/CRO will request additional information if needed and Check-Cap will report the event to the FDA within 10 working days of first notification of the event. The Investigator must notify their IRB of the event no later than 10 working days after learning of the vent.

	Document Title	Clinical Investigational Plan For Study CL-SY-02-0096		
	Document No.	DOC001593	Revision	03

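### Section 16 stops collecting adverse events once bowel preparation starts, with no exception for serious or device-related events; Section 16.3 says the opposite, and the primary outcome can lose events

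*Combined protocol and SAP*

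**What the plan says.** The second paragraph of Section 16 sets two exclusions. One is by time: "Any adverse events with an onset following beginning of bowel preparation to colonoscopy procedure will not be collected". The other is by cause: "Colonoscopy related adverse events are not part of the study, are considered standard of care and will not be reported".

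Two other places agree with the time rule. Section 16.4.1 has subjects asked about changes in their condition at "each study visit or phone call with the exception of Visit 2 for the standard of care Colonoscopy and the associated preparation procedure". The schedule in Section 5 and Table 1 in Section 13.1 mark adverse events at Visit 1, Follow-up 1 and Follow-up 2, and leave Follow-up 3 (the post-colonoscopy call) blank.

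Other places carry no time limit:

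- Section 16.3: "All anticipated and unanticipated adverse events will be collected and reported".
- Section 16.1.1 defines an adverse event as one "that appears or worsens during a clinical study, whether or not considered related to the device".
- Section 16.4.2: "Serious adverse events shall be reported to Check-Cap/Clinical Research Organization (CRO) in writing", within 24 hours of awareness.
- Section 16.4.3: "Unanticipated adverse device effects shall be reported to Check-Cap/CRO in writing", also within 24 hours.
- Section 10.3 defines the primary safety outcome as the "incidence of device or procedure related Serious Adverse Events (SAE), as adjudicated by the Independent Physician Adjudicator".

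**The concern.** The primary outcome is a count of related SAEs, and relatedness is for an independent physician to judge. The Section 16 cut-off acts before that judgement, because an event that is not collected cannot be adjudicated. The loss runs in one direction, toward a lower incidence, in a study whose stated purpose is to demonstrate safety.

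The rule may have been meant only to keep preparation and colonoscopy effects out of the data. The cause-based sentence beside it already does that for colonoscopy. As written, the onset rule goes further and also removes events that neither preparation nor colonoscopy caused.

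The sections also give sites conflicting instructions. One site could drop a post-preparation SAE under Section 16 while another reports it under Section 16.3 or 16.4.2, each following the protocol.

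**Working it through.** No stated figure is in question. Section 14.1.1 says the sample size of up to 45 is not power-based, and Section 14.1.4 plans descriptive statistics only. The check is therefore mainly of the text, with arithmetic for scale.

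**1. Which provisions limit collection by onset?**

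| Place | Onset limit |
|---|---|
| Section 16, second paragraph | Yes, from the start of bowel preparation |
| Section 16.4.1 | Yes, no questioning at Visit 2 or its preparation |
| Section 5 schedule; Table 1 in 13.1 | Consistent with a limit (Follow-up 3 blank) |
| Section 16.1.1, definition | None |
| Section 16.3, recording | None |
| Sections 16.4.2 and 16.4.3 | None |
| Section 10.3, primary outcome | None |

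No section says which prevails.

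**2. Can a related SAE begin after preparation starts?** The documents provide a route.

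- Section 13.7.1 lets the capsule procedure end on an auditory signal, without excretion.
- Section 15.1.3.1 accepts that a capsule may still be inside after the recorder indicates expulsion.
- Sections 15.1.3 and 15.1.3.1 foresee removal by colonoscopy.
- Section 8.1 describes a capsule removed at the follow-up colonoscopy in the earlier study.
- Section 12.2 requires a colonoscopy scheduled within 60 days and gives no minimum interval after the capsule.

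Events that began before preparation, including delay or retention already present, remain collectable.

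**3. Does a narrower reading help?** The cut-off could be read as an interval running from preparation to colonoscopy. Later events would then be dropped only if colonoscopy-related. That term is not defined and can take in harm from retrieving the capsule, so the gap remains.

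**4. Is Follow-up 3 covered?** The first paragraph of Section 16 has subjects asked at every visit or call, Section 11.1 applies the same follow-up after colonoscopy, and Section 16.4.1 exempts only Visit 2 and the preparation. All three imply a question at Follow-up 3, but neither table marks it. No scheduled question therefore clearly covers the time from Follow-up 2 to bowel preparation. The documents do not fix how long that is.

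**5. Scale** (exact Clopper-Pearson two-sided 95% intervals).

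- One related SAE among 45: 1/45 = 2.2% (0.06 to 11.8%). If it is not collected: 0/45 = 0% (0 to 7.9%).
- Earlier study (Section 8.1): three SAEs, two of them post-colonoscopy, all judged unrelated. Related SAEs in 63 completed procedures: 0/63 (0 to 5.7%).
- Post-colonoscopy SAEs: 2/63 = 3.2% (0.4 to 11.0%). Scaled to this study: 45 × 2/63 = 1.4, range 45 × 0.0039 = 0.2 to 45 × 0.110 = 5.0. This assumes both followed the study colonoscopy. With the 66 enrolled as denominator: 2/66 = 3.0% (0.4 to 10.5%).

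**6. Chance of reporting zero events.** Let p be the true related-SAE risk and f the share with onset after the cut-off. Both are assumptions; the documents give neither. The chance of observing none in 45 is (1 − p(1 − f))^45.

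| p | f = 0 | f = 0.25 | f = 0.5 |
|---|---|---|---|
| 2% | 0.98^45 = 40% | 0.985^45 = 51% | 0.99^45 = 64% |
| 5% | 0.95^45 = 10% | 0.9625^45 = 18% | 0.975^45 = 32% |

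**The case against.** The strongest defence is that the cut-off is deliberate and coherent. Section 16 opens with it, Section 16.4.1 repeats it and both tables reflect it. On this view Section 16.3 speaks to expectedness rather than time and applies within the window already set. There is a rationale too: the anticipated events in Section 16.2 (diarrhea, soft stool, cramps, nausea) overlap with plausible preparation effects, and a single-arm study cannot separate them well.

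The loss may also be rare. A suspected retained capsule leads to physician contact and possibly X-ray. Section 8.1 says the earlier retrieval and delay cases ended without incident. Section 8 reports no related SAE in more than 220 volunteers across capsule versions; 0/220 has an upper 95% limit of 1 − 0.025^(1/220) = 1.7%. Sections 16.4.2 and 16.4.3 might still bring a late SAE or UADE in.

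Several of these points stand. The expected loss is probably small, the earlier retrieval shows exposure rather than harm, and overlapping symptoms are a fair reason not to collect non-serious preparation effects. They do not remove the defect. If Section 16 governs, related SAEs can be lost. If Sections 16.3, 16.4.2 and 16.4.3 govern, they contradict Section 16. Symptom overlap does not justify dropping SAEs, for which the plan already has a relatedness scale (Section 16.3.2) and an adjudicator.

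**Conclusion.** The concern holds, and the text is wrong as written. Collection for the primary outcome is cut off by onset with no exception for the events that outcome counts, and other sections say otherwise. This should be corrected before enrolment because ascertainment of the primary outcome is incomplete and the sections conflict. It does not rest on a prediction that events will be lost.

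Loss is a possibility whose rate the documents do not give. One missed event would move the primary result from 2.2% to 0%, with the upper limit falling from 11.8% to 7.9%, and no stated criterion would be crossed. The earlier study could report its two post-colonoscopy SAEs as unrelated because it recorded them. If the Section 16 cut-off governs, this study would not collect such events and could not show whether they were related.

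**What to change.** Replace the onset cut-off in Section 16 with wording such as:

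> All SAEs, all UADEs, and any adverse event suspected to be related to the device, the capsule procedure or capsule retrieval are collected through study exit, whatever the time of onset. The Independent Physician Adjudicator identifies SAEs due solely to bowel preparation or colonoscopy; these are listed separately and not counted in the primary outcome.

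Then:

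- State that harm from capsule retrieval at colonoscopy goes to the adjudicator and is not excluded beforehand as colonoscopy-related.
- Leave non-serious events due solely to preparation or colonoscopy uncollected, as now.
- Mark adverse events at Follow-up 3 in Section 5 and in Table 1 of Section 13.1, covering the time since Follow-up 2.
- Bring Sections 16, 16.3, 16.4.1, 16.4.2 and 16.4.3 into agreement.

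The cost is a wording change, one question on a call already made, and about 1 to 2 more SAEs to adjudicate on the earlier study's figures (up to about 5). Some non-serious events will also need sorting by cause; the documents do not allow that number to be estimated. No visit or procedure is added, and clinical management is unchanged.
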